17.0	PROTECTION OF HUMAN SUBJECTS	38
17.	1 Privacy	39
17.2	Serious Adverse Event (SAE) Reporting	
	7.2.1	40
18.0	INFORMED CONSENT PROCEDURES	_
19.0	REFERENCES	43
20.0	APPENDICES	

List of Abbreviations

Abbreviation or Specialized Term	Definition
ADA	anti-drug antibody
ADCC	antibody-dependent cell-mediated cytotoxicity
AE	adverse event
ALT	alanine aminotransferase
APC	antigen presenting cells
AST	aspartate aminotransferase
CD	cluster of differentiation
CI	confidence interval
CIS	carcinoma in situ
C _{max}	maximum observed concentration
CNS	central nervous system
CR	complete response
CRC	colorectal cancer
CRF	case report form
CT	computed tomography
CTC	circulating tumor cells
CTCAE	Common Terminology Criteria for Adverse Events
CTLA-4	cytotoxic T-lymphocyte antigen 4
DC	disease control
DCR	disease control rate
DLT	dose-limiting toxicity
DNA	deoxyribonucleic acid
DR	duration of response
ECG	electrocardiogram
ECOG	Eastern Cooperative Oncology Group
ELISA	enzyme-linked immunosorbent assays
EMA	European Medicines Agency
EOI	end of infusion
EU	European Union
Fc	fragment crystallizable
FFPE	formalin fixed paraffin embedded
FTIH	First-time-in-human

Abbreviation or Specialized Term	Definition
GCP	Good Clinical Practice
GI	gastrointestinal
HCI	hydrochloride
HCV	hepatitis C virus
HIPAA	Health Insurance Portability and Accountability Act
HIV	human immunodeficiency virus
ICF	informed consent form
ICH	International Conference on Harmonisation
IDMC	Independent Data Monitoring Committee
IEC	Independent Ethics Committee
IFN	interferon
lgG1κ	immunoglobulin G1 kappa
IHC	immunohistochemistry
IL	interleukin
IM	immunogenicity
IRB	Institutional Review Board
irAE	immune-related adverse event
irRC	immune-related response criteria
IV	intravenous(ly)
IVRS	interactive voice response system
IWRS	interactive web response system
MAb	monoclonal antibody
MedDRA	Medical Dictionary for Regulatory Activities
MDSC	Myeloid derived suppressor cell
miRNA	micro ribonucleic acid
MMR	mismatch repair
mRNA	messenger ribonucleic acid
MRI	magnetic resonance imaging
MRSD	maximum recommended starting dose
MTD	maximum tolerated dose
NCI	National Cancer Institute
NOAEL	no-observed adverse-effect-level
NSCLC	non-small cell lung cancer

Abbreviation or Specialized Term	Definition
OBD	optimal biological dose
ORR	objective response rate
OS	overall survival
PBMC	peripheral blood mononuclear cell
PD	progressive disease
PD-1	programmed death 1
PD-L1	programmed death ligand 1
PFS	progression-free survival
PK	pharmacokinetics
PR	partial response
Q2W	every 2 weeks
RCC	renal cell carcinoma
RECIST	Response Evaluation Criteria in Solid Tumors
RFA	Radiofrequency ablation
RT	Radiation therapy
SAE	serious adverse event
SD	stable disease
SID	subject identification
SMC	Safety Monitoring Committee
SPD	sum of products of diameters
SRT	Safety Review Team
SUSAR	suspected unexpected serious adverse reaction
TIL	tumor infiltrating lymphocyte
TNF-α	tumor necrosis factor alpha
TSH	thyroid-stimulating hormone
ULN	upper limit of normal
US FDA	United States Food and Drug Administration
USA	United States of America
WFI	water for injection
WHO	World Health Organization
w/v	weight/volume

1.0 PROTOCOL SUMMARY AND/OR SCHEMA

Name of Investigational drug: Pembrolizumab

Title of Study: Single Arm Phase II Study to Assess the Efficacy of Pembrolizumab Plus Radiotherapy or Ablation in Metastatic Colorectal Cancer Patients

Study Centers: MSKCC

Study Period: 24 months Phase of Development: ||

Objectives:

The **primary objective** is Overall Response Rate in disease that is not ablated or radiated (Complete Response and Partial Response).

The **secondary objectives** are:

- 1. Safety and tolerability of Pembrolizumab plus radiotherapy (RT) or ablation
- 2. Overall Survival of pembrolizumab plus RT or ablation
- 3. Progression free survival rate at 1 year
- 4. Progression free survival rate at 2 years

The **exploratory objectives** are to evaluate biomarkers that may correlate with activity of pembrolizumab plus RT or pembrolizumab plus ablation in colorectal cancer (CRC), or prospectively identify CRC patients likely to respond to treatment.

Study Design: This will be a Simon two-stage design, phase II study. It will be conducted to determine the efficacy and safety of (1) pembrolizumab plus RT in subjects with metastatic CRC who are undergoing RT as standard therapy; and, (2) pembrolizumab plus ablation in subjects with metast atic CRC who are undergoing ablation as standard therapy. Eligible patients will have metastatic colorectal cancer and received at least two prior standard therapy for metastatic disease. Patients will be stratified according to eligibility for RT (cohort 1) or ablation (cohort 2). Patients in cohort 1 will have at least one locally advanced or metastatic lesion for which palliative RT is considered appropriate standard therapy, and at least one other measurable index lesion that will not undergo RT. Patients in cohort 2 will have at least one metastatic lesion for which palliative ablation is considered appropriate standard therapy, and at least one other measurable index lesion that will not undergo ablation. All subjects will undergo ablation or begin RT within 1 week prior to dose 1 of pembrolizumab. Subjects will receive pembrolizumab via IV infusion at 200 mg every three weeks (Q3W), and continue treatment Q3W until progression of disease, initiation of alternative cancer therapy, unacceptable toxicity, or other reasons to discontinue treatment occur, up to 24 months. Patients who had a prior response or stable disease without another reason to discontinue therapy may resume treatment for an additional 12 months upon disease progression. Repeat palliative RT in cohort 1, or ablation in cohort 2, will be permitted in select cases for the treatment of isolated lesions, provided a target lesion remains. Patients will be evaluated by physical exam and routine blood tests every three weeks during the study period. CT or MRI will be performed during screening, and then at 9 week intervals. Tumor measurements and deter mination of tumor responses will be performed according to RECIST 1.1. Subjects may continue to receive pembrolizumab beyond radiographic progression in the absence of clinical deterioration, and after discussion with the Principal Investigator. All subjects will be followed up to 2 years for survival or until the study closes. The primary endpoint of this trial is the response rate in CRC treated with RT plus pembrolizumab (cohort 1) or ablation plus pembrolizumab (cohort 2). A two-stage Simon"s optimal design will be employed to test the null hypothesis that the true response rate is ≤5% versus the alternative hypothesis that the true response rate is at least 25% with type I and II error rates of 10% each. Each cohort will be evaluated separately for this purpose. In the first stage, we will accrue 9 patients in each cohort. If 0 objective tumor responses (PR or CR) are observed among the 9 subjects treated in a cohort, then subject enrollment will be terminated in that cohort. If at least 1 response is observed among the 9 subjects treated in a cohort, then the study will be expanded to enroll a total of 24 treated subjects in that cohort. At the end of the study, if 2 or less objective tumor responses are observed in a cohort, then the study will be considered not worthy of further investigation in that particular cohort. If at the end of the study ≥3 tumor responses per RECIST 1.1 are observed in a cohort, then further investigation of pembrolizumab plus RT and/or pembrolizumab plus ablation will be considered worthwhile. The study will complete when all subjects have either progressed or discontinued from the study for other reasons. This study requires accrual of a minimum of 18 subjects and up to a maximum of 48 subjects if both cohorts are expanded to the second stage. The accrual time is estimated to be 2 years. Tumor biopsies for research purposes will be

mandatory in all patients. Pre-treatment biopsies will be obtained during fiducial placement for RT, at the time of ablation, or during a separate procedure. On treatment biopsies will be performed. 1 week after completing RT or undergoing ablation (of the radiated/ ablated lesion) and then 4 weeks after dose #1 of pembrolizumab (of a non-radiated/ ablated lesion). Tumor immunohistochemistry may be performed for PD-L1 expression and quantification of tumor infiltrating lymphocyte (TIL) subtypes, including CD8+ Tcells, CD4+ T-cells, Regulatory T-cells (Treg), and Myeloid Derived Suppressor Cells (MDSCs). Peripheral blood samples will be obtained in all patients at baseline then weeks 3, 6, and 9 for all Additional blood draws beyond week 9 are permitted based upon interesting clinic/immunological findings. Plasma may be analyzed for change in antibody responses to a broad panel of antigens (seromics). Flow cytometry may be performed for peripheral blood immune cell phenotype and their activation status, including CD8+ T-cells, CD4+ T-cells, Tregs, and MDSCs. The amount of PDL-1 expression, changes in immune cell repertoire and activation status within the tumor and peripheral blood as well as immune responses against specific tumor antigens will be correlated with clinical outcome in an exploratory manner in order to identify predictive makers for response, and to further our understanding of pembrolizumab plus RT, and pembrolizumab plus ablation in CRC.

Diagnosis and Main Criteria for Inclusion in the Study:

Inclusion Criteria

- 1. Willing and able to provide written informed consent.
- 2. Histologically- or cytologically- confirmed CRC.
- 3. Locally advanced or metastatic CRC.
- 4. Subjects have received at least two standard available therapies.
- 5. At least one tumor for which palliative RT is considered appropriate standard therapy (cohort 1); or, at least one tumor for which palliative ablation is considered appropriate standard therapy (cohort 2).
- 6. At least one index lesion that will not undergo RT or ablation, and is measurable based on RECIST 1.1.
- 7. ≥ 18 years of age on day of signing informed consent.
- 8. Consent for tumor biopsies and blood draws for research purposes.
- 9. Consent for use of available archived tissue for research purposes.
- 10. Performance status of ECOG 0 or 1.
- 11. Adequate organ function, defined as:
 - Absolute Neutrophil Count ≥ 1,500/mm³.
 - Platelet count ≥ 100,000/mm³.
 - Serum creatinine ≤ 1.5 x ULN or CrCl ≥60 mL/min.
 - AST and ALT ≤ 2.5 × ULN or ≤ 5 × ULN for subjects with liver metastases.
 - Bilirubin ≤ 1.5 × ULN or Direct bilirubin ≤ ULN.
 - INR/PT and PTT ≤1.5 X ULN unless on anticoagulant therapy and PT/PTT within therapeutic range.
- 12. Adequate method of contraception.

Exclusion Criteria

- 1. Currently participating in/ has participated in an investigational study within 4 weeks.
- 2. Diagnosis of immunodeficiency or is receiving systemic steroid therapy or any other form of immunosuppressive therapy within 7 days prior to the first dose of trial treatment.
- 3. Prior monoclonal antibody within 4 weeks prior to study Day 1 or who has not recovered (i.e., ≤ Grade 1 or at baseline) from adverse events due to agents administered > 4 weeks earlier.
- 4. Prior chemotherapy, targeted small molecule therapy, within 2 weeks prior to study Day 1 or who has not recovered (i.e., ≤ Grade 1 or at baseline) from adverse events due to a previously administered agent (exc. Grade 2 neuropathy).
- 5. If subject received major surgery, they must have recovered adequately from the toxicity and/or complications from the intervention prior to starting therapy.
- 6. Known additional malignancy that is progressing or requires active treatment. Exceptions include basal cell carcinoma of the skin, squamous cell carcinoma of the skin, or in s itu cervical cancer that has undergone potentially curative therapy.
- 7. Known CNS metastases and/or carcinomatous meningitis. Subjects with previously treated

brain metastases may participate provided they are stable without evidence of new or enlarging brain metastases, and are not using steroids for at least 7 days prior to trial treatment.

- 8. Active autoimmune disease requiring systemic treatment within the past 3 months or a documented history of clinically severe autoimmune disease, or a syndrome that requires systemic steroids or immunosuppressive agents.
- 9. Interstitial lung disease or active, non-infectious pneumonitis.
- 10. Active infection requiring systemic therapy.
- 11. History or current evidence of any condition, therapy, or laboratory abnormality that might confound the results of the trial, interfere with the subject participation for the full duration of the trial, or is not in the best interest of the subject to participate, in the opinion of the treating investigator.
- 12. Known psychiatric or substance abuse disorders that would interfere with cooperation with the requirements of the trial.
- 13. Pregnant or breastfeeding, or expecting to conceive or father children within the projected duration of the trial, starting with the pre-screening or screening visit through 120 days after the last dose of trial treatment.
- 14. Prior therapy with an anti-P D-1, anti-P D-L1, anti-P D-L2, anti-CD137, or anti-Cytotoxic T-lymphocyte-associated antigen-4 (CTLA-4) antibody (including ipilimumab or any other antibody or drug specifically targeting T-cell co-stimulation or checkpoint pathways).
- 15. Known history of Human Immunodeficiency Virus (HIV) (HIV 1/2 antibodies).
- 16. Known active Hepatitis B or C.
- 17. Live vaccine within 30 days prior to the first dose of trial treatment.

Number of Subjects: 18 to 48, including patients in cohort 1 (n=9 to 24) and cohort 2 (n=9 to 24).

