4.2 Intervention

Patients will be stratified according to eligibility for RT (cohort 1) or ablation (cohort 2). Patients in **cohort 1** will have at least one locally advanced or metastatic lesion for which palliative RT is considered appropriate standard therapy, and at least one other measurable index lesion that will not undergo RT. Patients in cohort 2 will have at least one metastatic lesion for which palliative ablation is considered appropriate standard therapy, and at least one other measurable index lesion that will not undergo ablation. Subjects in cohort 2 will undergo ablation of one or more lesions. The ablation method is at the discretion of the interventional radiologist. All subjects will undergo ablation or begin RT within 7 days prior to starting pembrolizumab. Pembrolizumab dosing may continue during RT. Subjects will receive pembrolizumab via IV infusion at 200 mg every three weeks (Q3W), and continue treatment Q3W until progression of disease, initiation of alternative cancer therapy, unacceptable toxicity, or other reasons to discontinue treatment occur, up to 24 months. Patients who had a prior response without another reason to discontinue therapy after 24 months will continue clinic visits, routine blood work (CBC, COMP, CEA) and CT/MRI every 9 weeks, and may resume treatment for an additional 12 months upon disease progression. Repeat palliative RT in cohort 1, or ablation in cohort 2, will be permitted in select cases for the treatment of isolated, non-target lesions. Patients will be evaluated by physical exam and routine blood tests every three weeks during the study period. CT or MRI will be performed during screening, and then at 9 week intervals. Tumor measurements and determination of tumor responses will be performed according to RECIST 1.1.

Subjects may continue to receive pembrolizumab beyond radiographic disease progression in the absence of clinical deterioration, and after discussion with the Principal Investigator.

All subjects will be followed up to 2 years for survival or until the study closes. Exploratory research studies to evaluate the effect of this therapy will be performed in patients using

research blood draws, and tumor biopsy at baseline, 1 week after completing RT or undergoing ablation (from the radiated/ablated lesion), and then 4 weeks after dose #1 of pembrolizumab (from a non-radiated/ablated lesion), for research purposes.

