10.0 EVALUATION DURING TREATMENT/INTERVENTION

Study Calendar

Period	Screening						Trea	tment			End of
Cycle ¹	4C	1	1	2	2	3	4	5	6	7+	study
Week	<6 weeks ²	0	1	3	4	6	9	12	15	18+	visit ¹⁵
Informed consent	Х										
Medical history	Х										
EKG	Х										
CT/MRI ³	х						х			х	х
Height ⁴	Х										
Physical examination	Х	Х		Х		Х	Х	Х	Х	х	Х
Vital signs/ Performance status ⁴	Х	х		х		Х	Х	Х	Х	х	х
Report medications	Х	х		х		Х	Х	х	Х	х	х
Pulse oximetry		Х		Х		Х	Х	Х	Х	х	Х
Report side effects				х		Х	Х	Х	Х	х	Х
CBC ^{5,6}	Х	Х		х		Х	Х	Х	Х	х	Х
Comp ^{5,7}	Х			х		Х	Х	Х	Х	х	Х
Thyroid function (TSH, fT3,fT4)	х					х		х		odd cycles	
CEA ⁸	х	х					х			х	х
Hepatitis B and C ⁹	Х										
Pregnancy test if female (Serum) ¹⁰	Х										
Research blood tests 5,11	Х			х		Х	Х				
Obtain archived tissue ¹²	Х										
Research tumor biopsy ¹³	Х		Х		х						
RT (Cohort 1) ¹⁴	Х										
Ablation (Cohort 2) ¹⁴	Х										
Pembrolizumab		х		х		х	х	х	х	х	

- 1. Each cycle is approximately 3 weeks in duration, corresponds to 1 completed treatment.
- 2. Procedures must be performed within 6 weeks prior to dose 1 of Pembrolizumab on Day 1.
- 3. CT or MRI will be performed during screening, then at 9 week (±1 wk) intervals and at final visit if more than 4 weeks from prior imaging. If patient is unable to receive CT contrast or the abdominal/ pelvic target lesion is indeterminate on CT then MRI with contrast (abdomen and pelvis) plus CT without contrast (chest) may be performed. Imaging may be delayed up to 2 weeks if patient is receiving additional RT or ablation.
- 4. Vital signs to include heart rate, respiratory rate, blood pressure, and weight.
- 5. Blood to be collected prior to dosing any study medications.
- 6. Hematology to include standard complete blood cell (CBC) panel.
- 7. Comprehensive metabolic panel included sodium, potassium, chloride, bicarbonate, BUN, creatinine, glucose, total protein, albumin, bilirubin, alkaline phosphatase, AST, ALT, calcium.
- 8. CEA to be obtained during screening, day 1 and then within two weeks (or on day) of subsequent imaging.
- 9. Serology for HepBsAg, HepBcAb and hepatitis C antibody (unless previously tested negative).
- 10. Serum pregnancy test is required within 2 weeks of starting radiation or ablation

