- Target Lesions All lesions up to a maximum of 5 lesions total (and a maximum of 2 lesions per organ) representative of all involved organs should be identified as target lesions. It may be the case that, on occasion, the largest lesion does not lend itself to reproducible measurement in which circumstance the next largest lesion which can be measured reproducibly should be selected.

• **Non-target Lesions** - It is possible to record multiple nontarget lesions involving the same organ as a single item on the case record form (e.g., "multiple enlarged pelvic lymph nodes" or "multiple liver metastases")

Response Criteria

Evaluation of Target Lesions

- **Complete Response** Disappearance of all target lesions. Any pathological lymph nodes (whether target or non-target) must have reduction in short axis to < 10 mm (the sum may not be "0" if there are target nodes).
- **Partial Response** At least a 30% decrease in the sum of the diameters of target lesions, taking as reference the baseline sum diameters.
- **Progressive Disease** At least a 20% increase in the sum of diameters of target lesions, taking as reference the smallest sum on study (this includes the baseline sum if that is the smallest on study). In addition to the relative increase of 20%, the sum must also demonstrate an absolute increase of at least 5 mm. (Note: the appearance of one or more new lesions is also considered progression.)
- **Stable Disease** Neither sufficient shrinkage to qualify for PR nor sufficient increase to qualify for PD, taking as reference the smallest sum of diameters while on study.

Evaluation of Non-target Lesions

- **Complete Response** Disappearance of all non-target lesions and normalization of tumor marker level. All lymph nodes must be non-pathological in size (< 10 mm short axis).
- **Non-complete response/Non-progressive disease -** Persistence of 1 or more non-target lesion(s) and/or maintenance of tumor marker level above the normal limits.

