The ORR is defined as the proportion of subjects CR or PR based on RECIST criteria. The exact 95% CI of ORR will be estimated using the binomial distribution. Progression-free survival will be measured from the start of treatment with pembrolizumab until the documentation of disease progression or death due to any cause, whichever occurs first. Progression-free survival will be censored on the date of last tumor assessment documenting absence of tumor progression for subjects who are still alive prior to data cutoff, dropout, or the initiation of alternate anticancer treatment. Subjects having no tumor assessments after the start of treatment with pembrolizumab will have PFS censored on the first date of treatment with pembrolizumab. Progression-free survival will be evaluated using the Kaplan-Meier method (Kaplan and Meier, 1958). Overall survival will be determined as the time from the start of

treatment with pembrolizumab until death. For subjects who are alive at the end of study or lost to follow-up, OS will be censored on the last date when subjects are known to be alive. The OS will be evaluated using the Kaplan-Meier method.

Safety and Tolerability Analyses

All recorded adverse events will be listed and tabulated by system organ class, preferred term and treatment. Any significant vital signs and clinical laboratory test results will be listed and summarized. Any significant physical examination findings, and clinical laboratory results will be listed.

Biomarker Analysis

Exploratory research studies will be done to evaluate the effect of this therapy will be performed using research blood draws and tumor biopsies at baseline, 1 week after completing RT or undergoing ablation (from the radiated/ablated lesion), and then 4 weeks after dose #1 of pembrolizumab (from a non-radiated/ablated lesion).

The pharmacodynamic effect of pembrolizumab and RT or ablation on Tumor Infiltrating Lymphocytes (TILs), such as CD4+ and CD8+ T-cells, and expression of tumor markers, such as PD-L1, will be assessed by summary statistics, and investigated graphically to explore patterns of change from pre-treatment to post-treatment specimens.

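### The synopsis and Section 4.2 differ on which lesions may receive repeat RT or ablation, and Sections 12 and 14 do not say how a target lesion treated on study is scored.

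*Combined protocol and SAP*

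**What the plan says.** Two sections of the protocol set the rule for repeat local treatment after pembrolizumab has started.

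- Synopsis (Section 1.0, Study Design): further local therapy, of the kind that the patient's cohort receives, "will be permitted in select cases for the treatment of isolated lesions, provided a target lesion remains".
- Section 4.2: the same treatment "will be permitted in select cases for the treatment of isolated, non-target lesions".

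The Section 10 study calendar (note 3) shows that the event is expected: "Imaging may be delayed up to 2 weeks if patient is receiving additional RT or ablation".

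The primary objective is "Overall Response Rate in disease that is not ablated or radiated". The rules that turn scans into endpoints do not repeat that restriction:

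- Section 12 defines PR as "At least a 30% decrease in the sum of the diameters of target lesions, taking as reference the baseline sum diameters".
- Section 12 defines PD as "At least a 20% increase in the sum of diameters of target lesions" from the smallest sum on study, with an absolute increase of at least 5 mm. New lesions also count as PD.
- Section 14: "The ORR is defined as the proportion of subjects CR or PR based on RECIST criteria".
- Section 14 censors PFS when another anticancer treatment starts. It does not say whether protocol-permitted repeat RT or ablation is such a treatment.

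**The concern.** The synopsis condition that a target must be left over has work to do only if a target may be treated. Treating non-target lesions could never use up the targets. Staff working from the synopsis and staff working from Section 4.2 could therefore treat different lesions.

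Inclusion criterion 6 does not remove the problem. It secures at least one measurable lesion that will not be treated, but says nothing about the other targets. A lesion can be a valid untreated target at baseline and be radiated or ablated later.

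If that happens and the full target sum is still used, shrinkage caused by the procedure enters the primary endpoint. The 5% null in Section 14 rests on the expectation that untreated lesions do not respond to current therapies, and a PR produced in a treated lesion falls outside that reasoning. PFS could also be lengthened if the procedure comes before the progression threshold is reached on a scan.

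**Working it through.** **1. The plan's own design.** Inputs from Section 14: p0 = 5%, p1 = 25%, stop at 0 of 9, total 24, go at 3 or more.

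P(go | p) = Σ over x = 1..9 of P[Bin(9,p) = x] × P[Bin(15,p) ≥ max(0, 3 − x)]

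At p = 0.05:
- x = 1: 0.29854 × 0.17095 = 0.05104
- x = 2: 0.06285 × 0.53671 = 0.03373
- x ≥ 3: 0.00836
- Sum: 0.0931

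At p = 0.25 the same formula gives 0.9028. Both meet the stated 10% error limits, so the design reproduces.

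**2. Effect of one treated target on the sum.** The lesion sizes are assumed. If the treated lesion is a share w of the baseline sum and shrinks by a fraction s, and the rest is unchanged, the sum falls by w × s. A PR needs w × s ≥ 0.30.

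| Baseline targets (mm) | After on-study treatment of one | Full sum | Untreated targets only |
|---|---|---|---|
| 40, 20 | 40 shrinks to 22, other unchanged | 42/60, −30%: PR | 20/20, 0%: SD |
| 30, 30 | one recorded as 0, other unchanged | 30/60, −50%: PR | 30/30, 0%: SD |
| 30, 30 | one recorded as 0, other grows to 42 | 42/60, −30%: PR | 42/30, +40%: PD |
| five of 20 | one recorded as 0, others unchanged | 80/100, −20%: SD | 80/80, 0%: SD |

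In the third row, had the first lesion not been treated and stayed at 30 mm, the sum would be 30 + 42 = 72 mm. Against 60 mm that is +20% and +12 mm, which is PD. The last row shows that the effect is not automatic.

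**3. Effect of one spurious response on the go rule.** All other patients respond at 5%.

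- In stage 1, the cohort always continues and needs 2 or more of the other 23: 1 − 0.95^23 − 23 × 0.05 × 0.95^22 = 1 − 0.30736 − 0.37206 = 0.321.
- In stage 2, the cohort must first pass on its own, then needs 2 or more true responses among the other 23: 0.29854 × (1 − 0.95^14) + P[Bin(9, 0.05) ≥ 2] = 0.29854 × 0.51233 + 0.07121 = 0.224.

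**4. Range for an assumed frequency.** Suppose a fraction q of true non-responders is counted as PR, so p = 0.05 + 0.95q. For q = 1%, 2%, 3%, 5% and 10%, P(go) is 13.7%, 18.6%, 23.9%, 35.0% and 60.6%. The documents give no value of q. The upper values fit poorly with treatment reserved for select cases.

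**The case against.** The strongest reply is that the two sections can be read together. A site that treats only non-target lesions satisfies both. Section 4.2 is the detailed intervention section, and the synopsis may simply be a looser summary. The primary objective already excludes treated disease, and the synopsis proviso fits an intention to judge response on whatever untreated target is left.

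Much of this stands:

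- If Section 4.2 governs, the target-sum route to a spurious PR disappears. What remains is smaller: a treated non-target lesion can still affect non-target CR or PD, and through PD it can affect PFS.
- A reader might infer that the protocol expressly permits treatment of target lesions. It does not. That follows from the proviso.
- A reader might infer that the plan keeps the reduced diameter in the sum. No sentence says so. Sections 12 and 14 are silent, and the full-sum result is what their definitions give when applied as written.
- A reader might infer that repeat treatment can erase progression. PD already documented, including by a new lesion, cannot be undone. Masking requires treatment before the threshold is recorded.

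The rest does not stand. The reviewed text gives no order of precedence between the synopsis and Section 4.2. The objective's restriction to untreated disease is not carried into the scoring rules for a lesion treated after baseline. The modifications of RECIST for immunotherapy mentioned in Section 14 are not specified, so they do not fill the gap.

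**Conclusion.** The inconsistency between the synopsis and Section 4.2 is real, and so is the missing scoring rule. Under the synopsis rule, one treated target that shrinks by at least 30% of the baseline sum can produce a PR with no change in untreated disease, and one such case can change a cohort's result.

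The figures of 32% and 22% are conditional on one spurious response having occurred. It would be wrong to read them, or the range in q, as the trial's actual type I error. As designed, that error is 9.3% per cohort, and the documents give no basis for how often a target would be re-treated. A spurious PR also needs a dominant treated target, no earlier PD and no new lesion.

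This is a gap that should be closed before the responses are counted. It is not a fault in the Simon design.

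**What to change.** 1. Reconcile Section 1.0 and Section 4.2 so that both state the same rule on which lesions may be re-treated. This review takes no position on which rule that should be.
2. Record the lesion and date of every on-study RT or ablation.
3. In Sections 12 and 14, state that from that date response and target-sum progression are assessed on the untreated target lesions only. The treated lesion is removed from the baseline, nadir and current sums. Shrinkage of a treated lesion, target or non-target, cannot contribute to CR or PR. PD documented before the procedure stands.
4. State whether repeat RT or ablation counts as another anticancer treatment for PFS censoring.
5. Add a sensitivity analysis that takes best response from assessments before the procedure.

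Two simpler rules are less suitable as the main analysis. Refusing any CR or PR after the procedure would discard true responses in the remaining untreated targets, which are what the trial is looking for. Freezing the treated lesion at its last diameter keeps treated disease in the denominator. With two 30 mm targets and one frozen, the other must grow by 20% of 60 = 12 mm (40%) to reach PD, against 20% of 30 = 6 mm if the treated lesion is removed.

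The cost is amendment wording, one CRF item, and fewer lesions in the sum for the affected patients. Sample size and decision rule do not change.
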